#### **Changes from Usual Treatment**

All laboratory tests and procedures undertaken in this study are for research purposes only, and would not be part of the usual clinical care of the subject. However, values of HbA1c and blood glucose exceeding normal levels will be reported to the participants and/or their primary care providers.

#### **E. Potential Scientific Problems:**

**Cohort Retention:** We have been able to retain study participants over an extended time period; 85% of the cases and 62% of the original cohort have been retained. Frequent telephone contact with well-trained and flexible staff has encouraged continued participation. Further loss to follow-up will be minimal because the majority of the population has already completed multiple visits and

drop-out is limited to moving out of the study area. We offer long-distance participation protocol which has significantly reduced drop-out rates.

**Limitations:** As the study participants get older, some potentially exciting studies become not feasible. For instance, participating families told us that collection of stool samples, of interest in microbiome research, would decrease their further participation. This area is better left to TEDDY that has collected monthly stool samples in young participants. We have also refrained from collecting T-cells, on a large scale, because of cost, poor performance of assays, and large blood volume needed relative to child's age. However, DAISY has participated in a number of smaller T-cell studies, using fresh blood (in collaboration with Drs. [name], [name], [name] and [name]) and we will strongly consider adding T-cell studies to the follow-up if our current collaborative experiments with Drs. [name] and [name] or others show promising results.

#### **F. Data Analysis Plan:**

Plan for monitoring adverse events: This is not a therapeutic/intervention study, and so we do not anticipate any adverse events. There will be no independent data safety monitoring board, since this is not a therapeutic or intervention study. The study coordinator and the Principal Investigator will conduct ongoing monitoring of the study.

#### **Specific Aim 1. Determine the natural history of islet autoimmunity and to explore the heterogeneity of diabetes and other autoimmune phenotypes in young adults through follow-up of the existing cohort for 5 more years.**

We will follow already established cohort of youth at high risk of T1D and other autoimmune diseases (current n=1149, median age 17.2 y, IQR 13.5-20.2 y). We will estimate overall burden of pre-clinical and clinical T1D, celiac, thyroid, adrenal, rheumatic and parietal autoimmune disease in Colorado by age 25. This will inform future screening and prevention programs. We will further explore the apparent heterogeneity of IA and its implications for adult-onset diabetes. Selected hypotheses include:

- Hypothesis 1.1: Persistent IA triggered after the age of 6 y results in T1D diagnosis in early adulthood
- Hypothesis 1.2: Transient childhood IA does not increase the risk of diabetes in early adulthood
- Hypothesis 1.3: Sedentary life-style and insulin resistance predict faster progression from persistent IA to T1D

**Statistical Analyses and Power** Cox PH analysis will be used to test Hypothesis 1.1 and 1.2, controlling for HLA-DR,DQ, family history of T1D, sex and ethnicity. Similarly, we will estimate adjusted hazard ratios (HR) for sedentary lifestyle and insulin resistance, adjusted for Tanner Stage and diet (Hypothesis 1.3). Assuming an additional 5% of children will seroconvert, we will have 80% power at a  $\alpha=0.05$  to detect  $HR>1.8$  or  $< 0.56$  /SD.

Joint latent class models. Using fixed and time-varying covariates from the 1-year period following conversion to IA, we will develop a joint latent class model that captures the dependencies between our fixed and longitudinal covariates (age, HLA risk group, family history, BMI, glucose, physical activity, insulin resistance, development of additional IAb) and time from IA conversion to T1D. We assume that heterogeneity across our cohort can be distilled into homogeneous latent subgroups with common covariate trajectories or patterns and common risk of T1D. We will implement the method using the *lcmm* R package, which will also allow us to summarize dynamic predictive accuracy of the joint model over time.

Analytic methods to examine age-related heterogeneity will include testing age\*exposure interaction terms with age as a continuous variable in a Cox PH model. If these are significant, suggesting violation of the assumption of proportionality, we will explore age cut-points using B-spline functions, and adjusting for variables found to be associated with IA in the previous investigation. We will then incorporate these age cut-points into the interactions terms in the proportional hazards model to test the age-related heterogeneity.

Power analysis. A two-sided log rank test with an overall sample size of 2,547 subjects (Hypotheses 1.1 and 1.2) with an overall IA rate of 9% in 15 years achieves 80% power at a 0.05 significance level to detect a HR=0.66 assuming that the proportion of children lost to follow-up is 0.20. These results are based on the assumption that the hazard rates are proportional over time. Adjusting for covariates in a Cox model and assuming that the regression of cohort membership on covariates has an R^2 of 0.5, the minimally detectable hazard ratio is 0.56. For the Hypothesis 1.3, among IA positive children (n=98), we will have 80% power to detect a hazard ratio of 1.87 for each SD increase in time spent sedentary, waist circumference, and BMI, assuming 20% of children with IA will develop T1D. Expected SDs: time spent sedentary=90 minutes/day; waist circumference=15cm; BMI=4.3 kg/m^2.

**Specific Aim 2. Validate candidate proteomic biomarkers of IA and T1D, in a nested-case study of 213 youth with persistent IA and 213 controls.**

Statistical analyses will be carried out by [name] (PNNL) – see letter of collaboration. The relative quantification data will be normalized to the reference sample, log transforming (base 2), and then median centered. First mixed effects linear models, with a normal conditional distribution and identity link function, will be fit separately to cases and controls using R and the lme4 package. Age and sex will be used as the fixed effects in these models including linear and quadratic models to examine trends in abundance over time and random effects for each subject will be included to account for the subject variability and non-independent nature of the data over time. Likelihood ratio tests will be conducted with ( $\alpha = 0.05$ ). A difference in trends between cases and controls will be quantified by fitting the mixed effects linear/quadratic models and including a fixed effect to account for different mean intercepts, slopes and quadratic terms, where applicable, for each group. Additionally, a likelihood ratio test between a model including and not including case-control status as an effect can be used to determine differences in intercept, slope, and/or quadratic mean trends. The highest degree model that is statistically significant for at least one group will be fit with fixed effects for age and group and an interaction term between age and group (allowing for separate slopes for each group) and a random effect for subject.

Detecting a significant difference in trends cases and controls is by testing if the group regression parameter is equal to 0, which is rejected when the true population parameter is different from 0. In the case of a linear trend, this involves the following t-test:  $t_{\alpha, n-4} = b/s_b$  where  $\alpha$  is the type 1 error rate,  $b$  is the estimated regression parameter,  $s_b$  is the standard error of the regression parameter estimate. The standard error of the regression parameter estimate depends on the overall variability of the data, the number of subjects (n) and the number of time points per subject (T). A power analysis was conducted based on a simulation study. From the previous DAISY1 study, the 75th percentile absolute value estimated slope due to group membership was  $b = 0.005$  and the overall error variances were calculated for each peptide. **Table 4** gives the power of the above test for select combinations of number of subjects and time points per subject for the 90th percentile of error variances. There will be a sufficient power to test the hypotheses with 4 or more samples per subject even in a subgroup analysis with 25 subjects per subgroup. For instance, a sample size of 20 subjects per group and 4 time points per subject will provide at least 82% power at the 90th percentile of the observed error variances.

Number of subjects/group	Number of time points/subject					
	3	4	5	6	7	8
30	.89	.99	1	1	1	1
25	.77	.90	.96	.99	1	1
20	.60	.71	.82	.89	.95	.98
15	.34	.43	.57	.52	.70	.84

The mixed model approach is typically preferred to ANCOVA with repeated measures for this type of data. ANCOVA's limitations include sensitivity to missing observations and restrictive variance-covariance structures. Additionally, mixed models naturally handle uneven spacing of

repeated measurements, tend to be more interpretable and will lead to natural tests for comparing groups.

**Quality Control and Protocol Adherence** for all specific aims will remain largely the same and include: standard interviewer training and retraining, inter-interviewer reliability testing; precisely written protocols, random review of the study forms by the investigators, computing error rates from doubly entered screens, blind duplicates for laboratory measures at a sampling rate of 5%, monthly QC logs of clinical and laboratory data, equipment calibration data, re-certification data, listing of incomplete exams, and adverse events. The distribution of data for key variables will be reviewed. Interviewers, examiners, and laboratories will be queried about unusual, illogical or out-of range values and missing values. The study investigators meet monthly.

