**Figure 4: Multiple phenotypes of childhood islet autoimmunity (IA) and their outcomes**

**Early IA:** may lead to a rapid progression to T1D or a classic presentation of T1D at school-age with a discernible remission.

**Late IA:** may lead the classic presentation of T1D or slowly progress to diabetes in adulthood.

Either early or late IA may remit without progression to diabetes, but may leave a  $\beta$ -cell defect contributing to type 2 diabetes in adults.

Late-onset IA, slowly progressing to diabetes, may lead to overt diabetes in adults, including classical T1D, LADA, GDM and phenotypes masquerading as T2D. It is unknown what proportion of adult diabetes represents slowly progressing or transient IA. The heterogeneity of diabetes in young adults poses a perplexing research and clinical challenge. Extended follow-up of DAISY participants for dysglycemia and diabetes will help to improve classification, diagnosis and possibly therapeutic targets for these patients.

Interestingly, the development of IA continues unabated beyond early childhood (Fig 1). This proposal will extend the incidence estimates to age 25 and will increase the precision of estimates by ~20%. IA levels fluctuate from positive to negative and back to positive in some children. While we do not fully understand the biological reasons for the remitting-relapsing course of IA, our findings show that a much larger number of children than previously thought have an extended period of IA, without rapidly progressing to T1D. These children may develop diabetes as adults or escape diabetes altogether by re-establishing tolerance to islet autoantigens. If the latter is true, understanding the pathomechanisms could greatly help development of prevention and, possibly, cure.

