### **Progression from Islet Autoimmunity (IA) to T1D**

Hypothesis 1.1: Persistent IA triggered after age 6 y results in T1D diagnosis in early adulthood

Hypothesis 1.2: Transient childhood IA does not increase the risk of diabetes in early adulthood

As of 10/2015, 94 children participating in DAISY follow-up have developed T1D. All but one had expressed IA prior to or at diagnosis. Over 70% of children expressing two or more autoantibodies progressed to T1D in 10 years since seroconversion, compared to 15% of those with one autoantibody. There was little difference in progression by family history of T1D or presence of the HLA-DR3/4,DQB1\*0302 genotype. PTPN22 and UBASH3A and INS predicted diabetes, controlling for family history of T1D and presence of HLA-DR3/4-DQB1\*0302 genotype. In general population children, risk alleles at these 5 genetic markers conferred combined HR of 13 for IA and >40 for T1D. INS, UBASH3A, and IFIH1 were significantly associated with progression from IA to T1D, while PTPN22 and IL27 showed a borderline association. Age of appearance of first autoantibody and mean IAA levels during the follow-up were major determinants of the age at diagnosis. In contrast, levels of GAA or IA-2A did not predict time to progression to diabetes.

***New assays for insulin/proinsulin and GAD autoantibody detection:*** Serial serum samples from DAISY participants followed from birth who progressed to T1D were essential in development of novel assays for insulin/proinsulin autoantibodies (IAA), GADA and TGA. These nonradioactive electrochemiluminescence-based assays have been developed on a platform from MesoScale Discovery (MSD). The ECL-IAA assay detects onset of IA earlier than any current standard radioassays in 24% of children, thus defining more precisely the onset of IA and timing of potential triggering events. Both ECL-IAA and ECL-GADA assays are more specific for high-affinity autoantibodies that predict progression to T1D. Next, the individual ECL assays were adapted to measure four antibodies in a single well using a small blood volume (6ul). Using a MSD QuickPlex 4-Spot plate or U-Plex plate, we successfully combined ECL-IAA, GADA and IA-2A with transglutaminase autoantibodies (ECL-TGA) in a single well of a 96 well plate. The multiplex ECL

[figure not shown]

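### Hypothesis 1.2 claims no increase in diabetes risk, but it is assigned an ordinary difference test and a power figure built on other events and another exposure, so a non-significant result could not support it

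*Protocol*

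**What the plan says.** In section IV.F (Data Analysis Plan), Specific Aim 1, the hypothesis reads "Transient childhood IA does not increase the risk of diabetes in early adulthood". Under Statistical Analyses and Power, the method is given in one sentence: "Cox PH analysis will be used to test Hypothesis 1.1 and 1.2, controlling for HLA-DR,DQ, family history of T1D, sex and ethnicity". Hypothesis 1.1, which asserts an effect, and Hypothesis 1.2, which asserts the absence of one, thus share one test.

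The Power analysis paragraph names both hypotheses and takes a two-sided log-rank test in all 2,547 children. Its event rate is worded "with an overall IA rate of 9% in 15 years", so the event counted is IA. The claim made for this design is that it "achieves 80% power at a 0.05 significance level to detect a HR=0.66". It assumes 20% loss to follow-up. It then regresses cohort membership on covariates with an R² of 0.5 and gives a detectable HR of 0.56. A separate power figure under Statistical Analyses and Power is expressed per standard deviation. It follows the sentence on Hypothesis 1.3 and does not concern transient IA.

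The protocol gives no equivalence or non-inferiority margin, no upper confidence limit and no rule for when Hypothesis 1.2 counts as supported. It does not define transient IA, name the comparator, or give the number of children with transient IA or the diabetes events expected among them and their comparators.

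**The concern.** The null of a Cox or log-rank test is HR = 1. Rejecting it upward refutes Hypothesis 1.2. Failing to reject it shows only that the data did not detect a difference, which can happen because there is none or because events are few. With no bound stated in advance, nothing in the plan separates these two cases.

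The question is open on the protocol's own account. The Figure 4 legend says "Either early or late IA may remit without progression to diabetes" and goes on to allow that a remaining beta-cell defect may contribute to type 2 diabetes in adults. The text below it says that the share of adult diabetes arising from slowly progressing or transient IA is unknown. An uninformative null here could be taken as support for the hypothesis. The power statement labelled for Hypotheses 1.1 and 1.2 might also lead a reader to think that the question is adequately powered.

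**Working it through.** **1. The plan's own power figure.** Inputs from the Power analysis paragraph: N = 2,547, IA rate 9%, loss 20%, two-sided alpha 0.05, power 80%.

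- Events = 2,547 × 0.80 × 0.09 = 183.4.
- Schoenfeld, equal split: events needed for HR 0.66 = (1.96 + 0.84)² / (0.25 × ln(0.66)²) = 182.
- Detectable HR with 183.4 events = exp(−2.80 / √(183.4 × 0.25)) = 0.661.
- With R² = 0.5, effective events = 91.7 and detectable HR = exp(−2.80 / √(91.7 × 0.25)) = 0.557.

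Both stated figures reproduce. The split may also be that of the two recruitment cohorts: with 1,424 of 2,547 from the general population, power at HR 0.66 is 79.8%. The arithmetic is sound, but it describes about 183 IA events compared across two groups of similar size. Hypothesis 1.2 concerns diabetes events in a transient-IA group of unstated size.

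**2. What an ordinary test could show for Hypothesis 1.2.** The documents supply neither the diabetes events in the comparison (D) nor the share with transient IA (p), so both are assumed.

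- Power = Φ(√(D·p·(1−p)) × ln HR − 1.96).
- Upper 95% limit when the estimate is HR 1 = exp(1.96 / √(D·p·(1−p))).
- No allowance is made for covariate adjustment, which would lower power further.

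| D | p | Power, HR 2 | Missed, HR 2 | Power, HR 3 | Upper limit if estimate is 1 |
|---|---|---|---|---|---|
| 10 | 5% | 7% | 93% | 11% | 17.2 |
| 10 | 10% | 10% | 90% | 18% | 7.9 |
| 20 | 5% | 10% | 90% | 19% | 7.5 |
| 20 | 10% | 15% | 85% | 31% | 4.3 |
| 40 | 5% | 16% | 84% | 33% | 4.1 |
| 40 | 10% | 26% | 74% | 55% | 2.8 |

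Worked example, D = 40 and p = 10%: √(40 × 0.1 × 0.9) = 1.897. Then 1.897 × 0.693 − 1.96 = −0.645, and Φ(−0.645) = 26%. The upper limit is exp(1.96 / 1.897) = 2.8.

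The approximation is rough with so few events. An exact conditional binomial test (one-sided 2.5%) gives power at HR 2 of 6% for the first row, 14% for D = 20 and p = 10%, and 30% for the last row. The picture is the same.

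**3. What excluding an increase would take.** With true HR 1, one-sided 2.5% and 80% power, events = (1.96 + 0.84)² / (p(1−p) × ln(margin)²). The margins are illustrations only, since the protocol names none.

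| Margin | p = 5% | p = 10% | p = 20% |
|---|---|---|---|
| 1.5 | 1,006 | 531 | 299 |
| 2 | 344 | 182 | 103 |
| 3 | 137 | 73 | 41 |

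For scale, the protocol counts 94 T1D cases in the whole cohort as of 10/2015.

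**4. A favourable case.** If all 94 T1D events entered the comparison with p = 10%, power would be 52% at HR 2 and 89% at HR 3. That requires a comparator that includes children with persistent IA.

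**The case against.** The strongest reply is that the protocol states no wrong decision rule. It states none, and an interpretation rule for one hypothesis of an observational cohort may sit in an analysis plan that is not shown. The Cox model yields a hazard ratio with an interval in any case, and the protocol reports intervals elsewhere, for example HR 3.8 (2.2–6.3) for siblings. Much of this is fair, and it limits the severity. It does not remove the point: the protocol itself chooses the test and attaches a power figure to Hypothesis 1.2, and neither suits the claim.

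Several stronger readings are tempting, but the documents do not support them.

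- A reader might infer that non-significance is nearly certain. It is likely for a true HR of 2 under the assumed counts. With 40 events and p = 10%, however, power reaches 86% at HR 5, and the favourable case above reaches 89% at HR 3.
- A reader might infer that a null result will be taken as proof. No passage says so.
- A reader might link the statement about informing screening and prevention programs to this hypothesis. In the protocol it follows, and refers to, the estimates of overall disease burden.
- Of the 94 T1D cases, "All but one had expressed IA prior to or at diagnosis". This suggests sparse T1D outside IA, but it describes cases diagnosed to date; the 89 in the Aim 2 case set had a mean diagnosis age of 9.6 years. Hypothesis 1.2 concerns diabetes in early adulthood, and the text at Figure 4 extends adult diabetes to non-classical forms, so this is not its event count.
- The 1.0% expected to be diagnosed as adults (Preliminary Studies) cannot serve as the reference risk. It is the remainder of the 1.4% who have T1D or multiple autoantibodies by age 15, not a rate in children without persistent IA.

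**Conclusion.** The point stands in limited form. The test and the power statement for Hypothesis 1.2 are built to detect a difference, so a non-significant result could not support the hypothesis. The stated HRs of 0.66 and 0.56 give no assurance about it, because they rest on IA events and cohort membership. That much follows from the text alone.

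The size does not. Missing a true HR of 2 in about 74 to 93% of studies, with upper limits of about 2.8 to 17 around an estimate of 1, depends on the assumed 10 to 40 diabetes events and 5 to 10% transient share. Severity is moderate: this is one of several selected hypotheses in an observational cohort, with IA as the primary outcome and T1D secondary.

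**What to change.** In section IV.F, Specific Aim 1, present Hypothesis 1.2 as estimation. Report the adjusted HR and the absolute difference in cumulative diabetes incidence, transient versus never IA, each with a 95% confidence interval; this needs a stated definition of transient IA. Say that a non-significant p-value will not be taken as support. Conclude that there is no increase only if the upper limit lies below a margin that the investigators state and justify before seeing the results; otherwise report the result as inconclusive.

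In the Power analysis paragraph, remove Hypothesis 1.2 or restate its part in terms of expected diabetes events and the expected number with transient IA.

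The cost is rewording two paragraphs, with no new data. The downside is that Hypothesis 1.2 will probably have to be reported as inconclusive.

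### The Hypothesis 1.3 Cox model leaves out autoantibody number and age at seroconversion, which the protocol itself ties closely to T1D; this costs some power and leaves the hazard ratios open to confounding of unknown direction

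*Protocol*

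**What the plan says.** Section IV.F, Specific Aim 1, first gives a Cox analysis for Hypotheses 1.1 and 1.2, "controlling for HLA-DR,DQ, family history of T1D, sex and ethnicity". For Hypothesis 1.3 it goes on: "Similarly, we will estimate adjusted hazard ratios (HR) for sedentary lifestyle and insulin resistance, adjusted for Tanner Stage and diet (Hypothesis 1.3". The sentence opens with a word that may or may not bring the earlier four covariates along. Neither list holds autoantibody number or age at seroconversion.

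The power paragraph of the same section says that among 98 IA-positive children, of whom 20% are assumed to develop T1D, "we will have 80% power to detect a hazard ratio of 1.87 for each SD increase in time spent sedentary, waist circumference, and BMI".

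Elsewhere the protocol describes what drives progression:

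- Progression from Islet Autoimmunity (IA) to T1D: "Over 70% of children expressing two or more autoantibodies progressed to T1D in 10 years since seroconversion", "compared to 15% of those with one autoantibody".
- Same subsection: "Age of appearance of first autoantibody and mean IAA levels during the follow-up were major determinants of the age at diagnosis".
- Same subsection, on two of the covariates that might be carried over (family history and the HLA-DR3/4,DQB1*0302 genotype): "There was little difference in progression by family history of T1D or presence of the" that genotype.
- Section III: late-onset IA presented with multiple autoantibodies less often than early-onset IA (15% against 32%) and progressed to T1D less often (p=0.01).

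**The concern.** The model that yields the Hypothesis 1.3 hazard ratios adjusts for pubertal stage and diet but not for two factors that the protocol singles out as prognostic. Both are already available, because islet autoantibodies are measured at every visit.

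Two things follow. First, leaving a strong prognostic factor out of a Cox model pulls the exposure hazard ratio towards 1 and lowers power, even when factor and exposure are unrelated. Second, if sedentary time, waist, BMI or insulin resistance differs by age at onset or autoantibody number among IA-positive children, the hazard ratio is also confounded. With about 20 expected events, a modest loss of power or a modest bias can decide whether Hypothesis 1.3 is reported as supported.

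**Working it through.** **1. The plan's own power figure.** Inputs from the power paragraph: n = 98, 20% events, hazard ratio (HR) 1.87 per SD, 80% power. Two-sided 0.05 is assumed for Hypothesis 1.3. For a continuous covariate in a Cox model, required events are D = (z₀.₉₇₅ + z₀.₈₀)² / [(ln HR)² (1 − R²)].

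- R² = 0: D = (1.960 + 0.842)² / (ln 1.87)² = 7.849 / 0.3918 = 20.03.
- Expected events: 98 × 0.20 = 19.6.
- Power: Φ(√19.6 × 0.626 − 1.960) = 79.1%. Detectable HR: exp(2.802 / √19.6) = 1.88.

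The stated figure is reproduced, but only with no allowance for any covariate, not even Tanner Stage and diet. An R² of 0.5 is given for Hypotheses 1.1 and 1.2; none is given for 1.3. With 19.6 events:

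| R² of exposure on covariates | Detectable HR | Power at HR 1.87 |
|---|---|---|
| 0.1 | 1.95 | 75% |
| 0.2 | 2.03 | 70% |
| 0.3 | 2.13 | 64% |
| 0.5 | 2.45 | 50% |

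**2. Strength of autoantibody number.** From the ten-year risks of 70% and 15%, under proportional hazards: HR = ln(0.30) / ln(0.85) = 7.4.

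That contrast may include children who became multiple-positive after seroconversion. For status at seroconversion a weaker effect is plausible:

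- Multiple at presentation (section III): (0.32 × 143 + 0.15 × 65) / 208 = 55.5 / 208 = 27%.
- Eventually multiple, assumed as the complement of the 46% who persistently have one autoantibody: 54%.
- Initially single children who become multiple: (0.54 − 0.267) / 0.733 = 37%.
- Their ten-year risk, assuming 70% and 15% by eventual status: 0.372 × 0.70 + 0.628 × 0.15 = 0.355.
- HR = ln(0.30) / ln(0.645), or about 2.7.

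**3. Effect of omission when exposure is independent of autoantibody number.** Simulated Cox models: n = 98, normal exposure, exponential event times, administrative censoring, 20% events, true HR 1.87, 2,000 to 3,000 runs.

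| Autoantibody HR | Share multiple | HR, omitted / adjusted | Power, omitted / adjusted |
|---|---|---|---|
| 7.4 | 54% | 1.77 / 1.88 | 68% / 74% |
| 7.4 | 27% | 1.73 / 1.92 | 66% / 76% |
| 2.7 | 27% | 1.84 / 1.89 | 73% / 75% |

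Repeat runs at 7.4 gave HRs of 1.72 to 1.80 and power of 62% to 70% when omitted, against 75% to 78% when adjusted. The power loss is therefore about 2 points (HR 2.7) to 13 points (HR 7.4).

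If 42% progress (the cohort to date has 94 T1D and 222 persistent IA) and the true HR is 1.5, the loss is about 19 to 22 points at 7.4 but only about 5 at 2.7.

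**4. Effect when exposure is related to both factors.** Assumptions, none from the protocol: 54% multiple with HR 7.4; HR 1.5 per SD for younger onset; exposure correlated at 0.2 with both, either towards higher risk or towards lower risk. 20% events.

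| Direction | True HR 1.0 appears as | False positives | True HR 1.87 appears as | Power, omitted / adjusted |
|---|---|---|---|---|
| Towards higher risk | 1.22 | 13% | 2.09 | 89% / 71% |
| Towards lower risk | 0.82 | 14% | 1.43 | 35% / 74% |

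With no correlation, the false-positive rate stays near 5%.

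**The case against.** - **The factors appear elsewhere in the plan.** This stands in part. Section IV.F also plans a joint latent class model for time from IA to T1D that includes age and later autoantibodies, and Cox models with age-by-exposure terms. Neither is stated to give the adjusted hazard ratios for Hypothesis 1.3, and the age-by-exposure terms do not bring in autoantibody number. A reader might infer that the plan ignores these factors altogether; it does not.
- **Covariate lists belong in an analysis plan.** A full list can wait. Here, however, the protocol names an adjustment set, and that set can be judged.
- **The independent-factor shift is not bias in the usual sense.** Correct: it reflects the non-collapsibility of the hazard ratio, and type I error is preserved. The loss of power is still real.
- **The 7.4 does not fit the proposed covariate.** This stands, and is why 2.7 is carried as the lower case. A reader might infer a loss of 20 points or so; that needs the stronger autoantibody effect, 42% events and a smaller true HR together.
- **Confounding towards the null is certain because older children are bigger and progress more slowly.** A reader might infer this, but the protocol gives no association between exposure and onset age or autoantibody number among IA-positive children. Tanner Stage takes up part of any age effect, and the Cox time scale is not stated. The protocol ties age at first autoantibody to age at diagnosis; only the late-onset comparison in section III bears directly on progression.
- **BMI and waist must be age-standardised.** This might be inferred from the SDs of 4.3 kg/m² and 15 cm. Those are power inputs, not a commitment to model raw values, so standardising is a preference.
- **About 20 events support few terms.** This stands and limits the fix.

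**Conclusion.** The point holds in moderate form. The stated Hypothesis 1.3 adjustment set omits two available factors that the protocol's own results mark as prognostic. The likely cost when exposure is independent of autoantibody number is modest at the planned 20% events: an estimate of about 1.72 to 1.84 for a true 1.87, and about 2 to 13 points of power. This rests on an autoantibody hazard ratio between 2.7 (assumed for status at seroconversion) and 7.4 (derived from the ten-year risks), and on 27% or 54% multiple-positive. Confounding is possible in either direction, and its size cannot be settled from the protocol. Separately, the 80% power at HR 1.87 makes no allowance for the adjustment that the plan already intends.

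**What to change.** In section IV.F, Specific Aim 1:

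1. Add to the Hypothesis 1.3 Cox model the number of autoantibodies (one against two or more), preferably as a stratum, and age at seroconversion as a continuous term.
2. Take autoantibody number at the start of the exposure risk period, so that later spread, a possible mediator, is not adjusted away.
3. State whether HLA-DR,DQ, family history, sex and ethnicity also apply to Hypothesis 1.3.
4. Restate power with a covariate allowance, for example about 70% at HR 1.87 with R² = 0.2.

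No new data are needed. The cost is one or two more terms with about 20 events (stratifying on autoantibody number saves one parameter) and some precision if onset age is strongly correlated with exposure. In that case the gain from the age term is removal of confounding rather than power.

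### The age cut-points are read from a spline and then tested in the same participants, after a significant test of the same question, so the final step is not a valid test of age-related heterogeneity

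*Protocol*

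**What the plan says.** The procedure is in the Protocol, section IV.F (Data Analysis Plan), Specific Aim 1, in the paragraph on age-related heterogeneity. It has three linked steps.

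1. Fit "interaction terms with age as a continuous variable in a Cox PH model".
2. "If these are significant, suggesting violation of the assumption of proportionality, we will explore age cut-points using B-spline functions", with adjustment for variables linked to islet autoimmunity (IA) in earlier work.
3. "We will then incorporate these age cut-points into the interactions terms in the proportional hazards model to test the age-related heterogeneity".

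The cut-points are therefore an output of step 2, and step 3 is called the test. The paragraph mentions no separate sample, no resampling and no adjusted critical value, and it does not label step 3 descriptive. The earlier work is cited for adjustment variables, not as a source of cut-points.

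**The concern.** An ordinary Wald test at an age cut assumes that the cut was fixed without sight of the outcome and that the test would have been done whatever the data showed. Neither holds here. The spline places the cut where the exposure effect appears to change in these participants, and step 3 is done only when step 1 has already found a significant age trend in the same data.

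At stake is what is reported after a positive step 1. A p-value from step 3 would look like added confirmation when it largely repeats step 1. Early-versus-late hazard ratios from that model would tend to be too far apart, with intervals that are too narrow.

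**Working it through.** **The plan's own figure first.** The power paragraph that follows does not concern the cut-point step, but it supplies the sample size and event count. Its inputs are "A two-sided log rank test with an overall sample size of 2,547 subjects", "with an overall IA rate of 9% in 15 years" and "assuming that the proportion of children lost to follow-up is 0.20".

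- Events: 2,547 × 0.09 × 0.80 = 183.4.
- Schoenfeld requirement for HR 0.66, equal groups, two-sided 0.05, 80% power: 4 × (1.960 + 0.842)² / (ln 0.66)² = 4 × 7.85 / 0.1727 = 182 events. Power with 183 events is 0.802.
- Covariate-adjusted HR with R² = 0.5: exp(−√(7.85 / (0.25 × 183.4 × 0.5))) = 0.557, against 0.56 stated.

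These figures reproduce and are not in question.

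**Simulation of the three steps.** From the protocol: N = 2,547 and about 183 events by age 15, with the 20% loss entered as a lower event count. Age is the time scale, which is what makes an age interaction a departure from proportionality. Assumed, because the protocol does not give them: step 1 at two-sided 0.05, one standard-normal exposure, a cubic B-spline with two inner knots, one cut within the central 80% of events, and two rules for reading the cut from the spline.

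Let y be the scaled Schoenfeld residual plus the overall log HR, with variance 1/V, and t the event age.

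- Step 1: z = Σ(t − t̄)y / √(Σ(t − t̄)² / V); passed if |z| > 1.96.
- Step 2: fit the spline to y and read off the cut, with c events before it and d − c after.
- Step 3: D = mean y after − mean y before; SE = √((1/V)(1/c + 1/(d − c))); significant if |D/SE| > 1.96.

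There were 8,000 runs with no heterogeneity (step 1 passed in 5.2%, 418 runs). There were 2,500 with a log HR rising linearly from −0.15 at birth to +0.15 at age 15 (passed in 20.6%, 515 runs). Monte Carlo error on the conditional percentages is about 2 points.

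| | Cut at largest spline contrast | Cut where spline crosses overall log HR | Cut fixed at 7 y (example) |
|---|---|---|---|
| *No true heterogeneity* | | | |
| Step 3 significant, step 1 ignored | 19.2% | 10.5% | 5.0% |
| Step 3 significant, step 1 passed | 83% | 68% | 54% |
| 95% CI covers truth, step 1 passed | 17% | 32% | 46% |
| Median ratio of HRs, step 1 passed (truth 1.00) | 1.51 | 1.42 | 1.34 |
| Steps 1 and 3 both significant | 4.4% | 3.6% | 2.8% |
| *Modest trend, true ratio about 1.16* | | | |
| 95% CI covers truth, step 1 passed | 64% | 79% | 89% |
| Median ratio of HRs, step 1 passed | 1.55 | 1.45 | 1.38 |

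Ratios are expressed as values above 1. With no heterogeneity, even the fixed cut without step 1 has a median of 1.11 on that scale, so 1.11 is the fair comparison for 1.51 and 1.42.

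**Two sources.** Choosing the cut from the data raises the error of step 3 from 5.0% to 10.5-19.2% before any screening. Screening by step 1 alone, with a fixed cut, raises it to 54%. Together they give 68-83%.

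**The case against.** The strongest reply is that the decision on heterogeneity is already protected. Step 1 is a valid test and comes first, so a false claim through steps 1 and 3 together arises in only 3.6-4.4% of null runs. That stands. A reader might infer that the whole procedure has an inflated error rate per exposure; it does not.

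Second, the work is exploratory. Aim 1 sets out to explore heterogeneity, age-varying exposure effects are not among Hypotheses 1.1-1.3, and the paragraph itself says "we will explore age cut-points using B-spline functions". That lowers the stakes. But exploring is the word used for finding the cut-points, and testing is the word used for the step that follows.

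Third, the paragraph promises no hazard ratios or intervals from step 3, and how intervals are built may be left to a statistical analysis plan. That stands too, so the point about estimates applies only to any that are taken from this step. The test itself is stated in the protocol.

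Fourth, the size rests on assumptions. A reader might infer that step 3 always confirms step 1 and that its interval never contains the truth. That does happen if the cut is chosen to maximise the standardised contrast directly, but the protocol states no such rule. Cuts read from a spline give the less extreme figures above.

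Finally, a reader might infer that the study's claim of different predictors for early and late IA rests on these hazard ratios. The documents do not support this. Section III (Preliminary Studies/Progress Report) and the Innovation text under Aim 1 present that claim as already found, from comparisons split at age 7 and from earlier spline analyses.

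**Conclusion.** The point holds for the last step only. Step 1 is sound and keeps a false heterogeneity finding at or below about 5% per exposure. Step 3, as worded, is neither an independent nor a valid test, and its nominal p-value should not be read as confirmation.

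Under the stated assumptions (first test at 0.05, one exposure, one cut, two inner knots), with no heterogeneity and step 1 passed, step 3 is significant in about 68-83% of runs instead of 5%, and its 95% interval covers the truth in about 17-32%. With a modest true trend (ratio of HRs about 1.16), the median estimate is about 1.45-1.55 and coverage is 64-79%. Other knots, cut rules or significance levels would change these figures. The direction was the same under both cut rules, because part of the distortion comes from the data-chosen cut and part from reaching the step only after a significant result.

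**What to change.** - Name the continuous age-by-exposure interaction, or the joint spline interaction, as the test of age-related heterogeneity.
- Show the age-varying hazard ratio as a spline curve with its confidence interval.
- Label hazard ratios at data-chosen cut-points descriptive. Take any interval for them from a bootstrap that repeats the whole sequence, including the first test. Repeating only the cut-point search is not enough.
- Alternatively, fix the cut-points in advance and report the estimates whether or not the first test is significant. In the simulation, a fixed cut reported without that screen had 5.0% error and 95% coverage; after the screen it did not. The ages of 4 and 8 years in section III came from splines in this same cohort, so adopting them would still reuse data.

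The cost is a change of wording and some computing, with no new data. The cut-point results lose their confirmatory p-value.
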